### c. Treatment time

- i. We have 3 times recorded for each patient at the level of each fraction
  - 1. Activity time
    - This is the time until treatment start (while patient is being set up for treatment), and is the window during which IGRT would be acquired
    - b. We will need to account for small percentage (~4%) of missing data in activity time
  - 2. Treatment start (won't really use this)
  - 3. Treatment end
- ii. Create variable to calculate "total treatment time" (treatment end activity time start)
  - 1. Total treatment time = activity (set up) time + treatment time
- iii. Following comparisons needed with 95% CI and p values:
  - 1. Change in activity time between pre and post intervention periods
    - a. Calculate this separately for PCAM vs. satellites
      - i. PCAM: pre intervention (2/10/16-2/9/17) vs. post intervention (3/10/17-10/10/17)
      - ii. Satellites: pre intervention (2/10/16-2/9/17) vs. post intervention (7/10/17-10/10/17)
    - Change in activity time between PCAM (intervention group) and satellites (control group) during first intervention period (3/10/17-6/9/17)
    - 3. Change in **total treatment time** between pre and post intervention periods
      - a. Calculate this separately for PCAM vs. satellites
        - i. PCAM: pre intervention (2/10/16-2/9/17) vs. post intervention (3/10/17-10/10/17)
        - ii. Satellites: pre intervention (2/10/16-2/9/17) vs. post intervention (7/10/17-10/10/17)
    - Change in total treatment time between PCAM (intervention group) and satellites (control group) during first intervention period (3/10/17-6/9/17)

## d. Cost analysis

i. We will evaluate radiotherapy-related expenditures during the course of radiotherapy, calculated according to prior methods by summing the reimbursement of claims for radiotherapy simulation, planning, physics, delivery, and management (Current Procedural Terminology [CPT] codes 77261 and 77999).[1] Because patients have a mix of commercial and government insurers, we will utilize the national Medicare base rate to normalize reimbursement for each CPT code, and in secondary analyses will utilize actual claims paid reimbursements. We will compare adjusted mean expenditures between the intervention and usual groups using generalized linear models with gamma distribution and log-link function. We will estimate adjusted mean differences by first exponentiating the model-based linear predictions for the average intervention and usual care groups separately and then calculating their arithmetic difference.

- ii. CPT codes
  - 1. G6002
    - a. This will capture all KV imaging with any modality
  - 2. 77014 (with the 26 modifier attached)
    - a. This will capture all CBCT imaging with any modality

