#### 8.2 Procedures

Data on use of daily imaging will be obtained from Aria. De-identified patient-level demographic and disease-specific data will also be obtained from EPIC, including patient age, race, gender, cancer diagnosis, and insurance provider. Billing information associated with the IGRT CPT codes used in the pre and post-intervention radiation courses will be obtained from our revenues department.

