### b. Secondary Outcomes

- i. Rate of images per total fractions (outcome as continuous variable)
  - 1. Change in rate of images per total fractions taken pre and post intervention in each arm
- ii. Multivariate analysis for factors associated with reduction in daily IGRT
  - 1. Cohort (intervention vs. control arms)
  - 2. Age
  - 3. Sex
  - 4. Race
  - 5. ECOG
  - 6. Insurance type (Commercial, Medicare , Medicaid, Uninsured, Unknown)
  - 7. Target type (Brain, bone, soft tissue, multiple sites, other)
  - 8. Prior radiation (course 1 vs. not course 1)
  - 9. Total number of fractions per course
  - 10. Dose per fraction
    - a. [name] will send us a distribution of this data and we will bucket it accordingly.
  - 11. Attending
  - 12. Time of day
  - 13. Location (PCAM vs. satellite)
- c. Exploratory Analyses
  - i. Change in treatment time (in minutes)
    - 1. Change in total treatment time between pre- and post-intervention periods in each arm
  - ii. Cost analysis
    - 1. Change in cost before and after intervention implemented in each arm
      - Use CPT codes (charges) and Medicare standardized reimbursements to determine change in healthcare costs pre and post default intervention

Analysis Plan – Reducing Daily Palliative IGRT

Commented [SS1]: Insurance status is from the Epic output as follows: Unknown, Blue Shield, Commercial, Managed Care, Managed Medicaid, Managed Medicare, Medicaid, Medicare, Self pay. These can probably be further consolidated - Perhaps: unknown, self pay, (Blue shield+commercial+managed care), (Managed Medicaid+Medicaid), (Managed medicare+medicare).

3

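### The expenditure sum defined in the SAP's cost analysis contains neither imaging code listed beneath it, and the SAP does not say how the two lists combine

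*SAP*

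**What the plan says.** The cost analysis is listed in the SAP under Outcome measures, Exploratory Analyses. The instruction there is broad: "Use CPT codes (charges) and Medicare standardized reimbursements to determine change in healthcare costs pre and post default intervention". No code list is attached to it.

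The operational definition is in Analysis Plan 2.d. Item i obtains expenditure by "summing the reimbursement of claims for radiotherapy simulation, planning, physics, delivery, and management", and gives the codes as "delivery, and management (Current Procedural Terminology [CPT] codes 77261 and 77999". It prices each code at a national Medicare rate, with reimbursements actually paid used in secondary analyses. It then compares the groups with a generalized linear model using a gamma distribution and log link.

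Item ii, under the same heading, lists two imaging codes. For G6002 it says "This will capture all KV imaging with any modality". For "77014 (with the 26 modifier attached") it says "This will capture all CBCT imaging with any modality". It says nothing about what is then done with the claims under these codes.

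On data, Protocol 8.2 states: "Billing information associated with the IGRT CPT codes used in the pre and post-intervention radiation courses will be obtained from our revenues department".

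**The concern.** The default order sets leave out daily imaging, so the most direct effect on cost should come through imaging claims. The only expenditure sum the SAP defines, and the only one linked to a model, is built from a code set that excludes both of the SAP's own imaging codes. An analyst who programmed 2.d.i as written could report little or no change in expenditure even if KV and CBCT claims had fallen.

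Cost is part of the trial's rationale (Protocol 2) and is among the benefits claimed in Protocol 11.6.2 and 11.6.3. This analysis is where that claim would be examined. The secondary analysis with paid reimbursements has no code list of its own, so it carries the same gap. An open code set also leaves room to settle the definition after the results have been seen.

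**Working it through.** No sample size, power or event count is involved. The check is whether the imaging codes belong to the defined set.

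**Inputs**
- Code set in SAP 2.d.i: 77261 and 77999. Reading A is these two codes only. Reading B is the range 77261 to 77999.
- Imaging codes in SAP 2.d.ii: G6002 (KV) and 77014 with the 26 modifier (CBCT).

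**Membership**

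| Code | Reading A | Reading B |
|---|---|---|
| G6002 | not included | not included: the letter prefix puts it outside any numeric range |
| 77014 | not included | not included: 77261 − 77014 = 247 below the lower limit |

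Reading A is also hard to square with the sentence it sits in, since two codes would have to stand for five service categories. Reading B is the more natural one, but the text does not state it. Image guidance is not one of the five categories, so the category names do not bring the imaging codes in either.

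**Effect on the cost contrast**

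In unadjusted means, write the group difference in course expenditure as

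D(full) = D(2.d.i codes) + D(imaging),

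D(imaging) = p(KV) × Δn(KV) + p(CBCT) × Δn(CBCT),

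where p is the Medicare rate for the code and Δn is the difference in mean claims per course. If 2.d.i is followed literally, the reported quantity is D(2.d.i codes), and the share of D(imaging) counted is 0 by construction. The documents give no rate p, no number of imaging claims per course and no total expenditure. D(imaging) therefore cannot be computed in money or as a fraction of the total.

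**Why the 0.2 in Protocol 9 does not supply the missing figure**

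That figure is the assumed fall in the probability of daily imaging. SAP 4.a defines daily IGRT as imaging on at least 80% of fractions.
- A course imaged on 3 of 5 fractions (3/5 = 60%) is not daily but still has three imaged fractions.
- A course that goes from 5 of 5 to 4 of 5 (4/5 = 80%) loses an image and remains daily.

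A change in the binary endpoint thus fixes neither how many courses lose imaging claims nor how many claims are lost.

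**The case against.** The strongest reply is that the cost analysis is the whole of 2.d, not item i alone. The two imaging codes stand under that heading and are said to capture all KV and all CBCT imaging. The obvious reason to list them there is to count their cost. The outcome list restricts no codes, and Protocol 8.2 plans to obtain IGRT billing. Item i also follows a cited earlier method, which may define the code set more fully, and the word joining the two codes may be a slip for a range. Finally, the analysis is exploratory.

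Much of this stands. An intention to include imaging is plausible. A reader might infer that the trial's cost outcome definitively leaves imaging out; the documents do not support that, because 2.d.ii points the other way. What does not stand is that 2.d.ii settles the matter. It says what each code captures. It does not say whether the claims join the sum, form a separate outcome or only identify imaging. Neither the outcome list nor Protocol 8.2 supplies the rule.

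Three other inferences go too far:
- That the analysis could show no saving at all. The documents do not list what lies between 77261 and 77999. They show only that the two named imaging codes lie outside.
- That a 20-point fall in daily IGRT means imaging claims vanish from 20 in every 100 courses. The 80% threshold rules out that conversion.
- That the gamma model would fail on courses with no imaging cost. The SAP applies it to summed radiotherapy expenditure and proposes no gamma model of imaging cost alone.

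**Conclusion.** The point holds as an internal conflict in the SAP. The modelled expenditure in 2.d.i excludes both codes in 2.d.ii on either reading of its code set, and no sentence joins the two items. Followed literally, claims under G6002 and 77014-26 contribute nothing to the cost comparison; that zero is exact. Its consequence for total expenditure is unknown, because the documents give no prices and no claim counts. The conclusion assumes only that 2.d.i is programmed as written and that 2.d.ii is not read as silently adding to it.

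The reach is limited. Daily IGRT use (primary) and images per fraction (secondary) do not depend on billing codes. The correction is still worth making before the cost data are analysed, because the stated rule can give a misleading cost contrast and is easy to put right.

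**What to change.** In SAP Analysis Plan 2.d:
- State whether the two codes in item i are the ends of a range and, if so, write it as 77261 through 77999.
- Define course expenditure as that range plus G6002 and 77014 with the 26 modifier, priced at the national Medicare base rate. Keep the modifier, since dropping it changes which claims count.
- Apply the same code set to the secondary analysis of paid reimbursements.
- Report the imaging component (G6002 plus 77014-26) separately, as a descriptive figure by arm and period.

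If the investigators instead intend imaging cost as an outcome of its own, the SAP should say so and specify its analysis.

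The cost is a sentence or two of text. Protocol 8.2 already provides for the IGRT billing data. It does not name claims for the five categories in 2.d.i, so the billing request should be checked to confirm that it covers both sets.

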#### 3. Adjusted Analysis

- a. Primary model
  - i. Adjust for:
    - 1. Intervention
    - 2. Attending (clustering at level of attending)
    - 3. Location (PCAM vs. Satellites)
    - 4. Time

#### b. Primary model + relevant patient level factors

- 1. Intervention
  - 2. Attending (clustering at level of attending)
  - 3. Location
  - 4. Time?
  - 5. Age
  - 6. ECOG
  - 7. Prior radiation
  - 8. Insurance type (Commercial, Medicare , Medicaid, Uninsured, Unknown)
  - 9. Total number of fractions per course
- c. Sensitivity model
  - i. Covariates:
    - 1. Cohort (intervention vs. control arms)
    - 2. Age
    - 3. Sex
    - 4. Race
    - 5. ECOG
    - 6. Insurance type (Commercial, Medicare , Medicaid, Uninsured, Unknown)
    - 7. Target type (Brain, bone, soft tissue, multiple sites, other)
    - 8. Prior radiation (course 1 vs. not course 1)
    - 9. Total number of fractions per course

Commented [SS6]: Time defined as days from intervention?

- 10. Dose per fraction
- 11. Attending
- 12. Time of day
- 13. Location (PCAM vs. satellite)
- d. Assess missing data
- e. Unadjusted and adjusted analyses for covariates in relation to primary outcome (daily IGRT use)

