#### i. Intervention arm (Perelman Center for Advanced Medicine - PCAM)

- 1. 2/10/2017-3/9/2017: 1 month roll out
  - a. Intervention announced to entire group at faculty meeting and by email
  - b. Individual meetings with intervention group attendings to assure awareness and use of default prescription order
  - c. Educational meetings with therapists to introduce new default prescription
- 2. 3/10/2017-6/9/2017: 3 month intervention period
  - Only the intervention arm (PCAM) has access to the default option and the usual practice group (satellites) does not undergo the intervention
- 3. 6/10/2017-10/10/2017: Crossover period
  - a. Default intervention is introduced to usual care group.
- Intervention group continues to practice without any change.
- ii. Usual practice / control group (Pennsylvania Hospital, Chestnut Hill,

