#### Doylestown, Valley Forge)

- 1. 2/10/2017-6/9/2017: Control period
  - Usual practice group does not undergo intervention and serves as control to intervention group during this time
- 2. 6/10/2017-7/9/2017: 1 month roll out
  - a. Intervention announced to usual practice group at faculty meeting and by email
  - b. Individual meetings with usual care group attendings to assure awareness and use of default prescription order
  - c. Educational meetings with therapists to introduce new default prescription
- 3. 7/10/2017-10/10/2017: 3 month intervention period

a. Both arms undergo the intervention

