# 2. Unadjusted Analysis

- a. Daily IGRT
  - i. Calculate daily IGRT use during pre-intervention period (2/10/16-2/9/17)
    1. Display graphically by month and cohort (PCAM vs. satellites)
  - ii. Calculate daily IGRT use at PCAM and satellites after intervention implemented (2/10/17-10/10/17)
    - 1. Display graphically by month and cohort (PCAM vs. satellite)
    - 2. Indicate on graph when intervention occurred at PCAM (2/10/17) and satellites (6/10/17)
  - iii. Conduct statistical analysis of change in daily IGRT pre and post intervention with 95% CI and p values
    - 1. Change in daily IGRT use from baseline pre-intervention period to intervention periods in both the control and intervention arms
      - Intervention group: Pre-intervention period (2/10/16-2/9/17) use of daily IGRT vs. Post-intervention period (3/10-17-10/10/17) use of daily IGRT
      - Control group: Pre-intervention period (2/10/16-6/9/17) use of daily IGRT vs. Post-intervention period (7/10-17-10/10/17) use of daily IGRT
    - Change in daily IGRT use during first intervention period (3/10/17-6/9/17) between usual care group (control) and intervention arms

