#### Methods:

For the main analysis model, we used PROC GENMOD to fit models based on generalized estimating equations with a logit link and an independence correlation structure using the attending physician as the clustering unit with month and site as covariates. In sensitivity analyses, the main model was estimated by also adjusting for patient characteristics including age, sex, race,...,..,etc.

To obtain the adjusted difference in the percentage of patients receiving daily IGRT imaging between intervention and non-intervention groups and 95% confidence intervals (CIs), we used the bootstrap method, resampling patients 1000 times. Resampling of patients was by physician to maintain clustering at the physician level. All analyses were conducted in SAS version 9.4.

7

**Commented [SS7]:** CR: Note: It's possible we might use a different correlation structure. We can modify what goes in the list of the covariates for the sensitivity model.

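### The SAP's sensitivity model 3.c leaves out intervention received and calendar time, enters PCAM versus satellite twice, and disagrees with the SAP's own Methods text

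*SAP*

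**What the plan says.** SAP Analysis Plan 3.a, the primary model, adjusts for intervention, attending (as the clustering unit), location and time. Model 3.b adds patient-level factors to these, with a question mark after time.

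Model 3.c, the sensitivity model, is a separate list of 13 covariates. The first is "Cohort (intervention vs. control arms" and the last is "Location (PCAM vs. satellite". Between them are patient and course characteristics, attending (without the clustering note used in 3.a and 3.b) and time of day. The same 13 items in the same order appear under secondary outcome 4.b.ii, titled "Multivariate analysis for factors associated with reduction in daily IGRT".

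The SAP ties arm and cohort to site in several places:

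- Section 2 (Study arms) heads one arm "Intervention arm (Perelman Center for Advanced Medicine - PCAM" and names the four satellites as the control group.
- Unadjusted Analysis 2.a.i asks the analyst to "Display graphically by month and cohort (PCAM vs. satellites".
- Section 2 also says of the final period, from 7/10/2017, "Both arms undergo the intervention".

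The Methods section describes the main model as a GEE logistic model clustered on attending, with month and site as covariates. It then says: "In sensitivity analyses, the main model was estimated by also adjusting for patient characteristics including age, sex, race". A margin comment there notes that the sensitivity covariate list can still be modified.

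Protocol section 9 keeps exposure and group apart. It lists a dummy for receiving the intervention alongside group and time, and makes that dummy's coefficient the one of interest.

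**The concern.** A sensitivity analysis should re-estimate the primary quantity under a different adjustment. Both groups start unexposed and both end exposed, so a fixed arm label does not measure exposure. Without a time-varying intervention term, model 3.c has no coefficient for the effect of the default, and without calendar time it has no protection against a secular trend.

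The SAP therefore defines its sensitivity analysis in two ways. An analyst who follows the Methods text gets a patient-adjusted re-estimate of the intervention effect. One who follows the 3.c list gets a PCAM-versus-satellite contrast that cannot be compared with the primary estimate but could easily be reported as if it could.

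The Methods text does not settle 4.b.ii, which has a further problem. Each course falls in one period only, so the main effects in such a model describe the level of daily IGRT use. That is how Adjusted Analysis 3.e words it: "Unadjusted and adjusted analyses for covariates in relation to primary outcome (daily IGRT use". They do not describe what predicts a reduction, which is what 4.b.ii promises.

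**Working it through.** The documents give no figure to reproduce here, because the point is one of model specification. The check compares the lists, then the rank of the design, then illustrates the consequence.

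**1. Terms listed**

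| Term | 3.a | 3.b | 3.c and 4.b.ii | Methods (sensitivity) |
|---|---|---|---|---|
| Intervention received | yes | yes | no | implied, not named |
| Calendar time | yes | yes, queried | no (time of day only) | month |
| Site | once | once | twice (Cohort, Location) | once |
| Attending | clustering | clustering | listed, role not stated | clustering |

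**2. Rank**, on the SAP calendar with each group's own roll-out month excluded

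- Intercept + Cohort + Location: rank 2 of 3. One term is aliased.
- If Attending is entered as dummies for about 29 physicians (protocol 5.3), each belonging to one group (protocol 5.1), the columns are 1 + 28 + 2 = 31 and the rank is 29. Neither group term is estimable.
- Intercept + intervention + location + 20 month levels: 1 + 1 + 1 + 19 = 22 columns, rank 22. Adding Cohort gives rank 22 of 23.

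**3. Exposure carried by the group label**

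Days from the SAP dates: pre-intervention 366, PCAM roll-out 28, first period 92, satellite roll-out 30, second period 93.

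- PCAM exposed share: (92 + 30 + 93) / (366 + 92 + 30 + 93) = 215/581 = 37.0%
- Satellite exposed share: 93 / (366 + 28 + 92 + 93) = 93/579 = 16.1%

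The label therefore separates the groups by only about 21 points of exposure.

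**4. What a group-only contrast would show**

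Baselines from protocol Table 2: PCAM 81.4%; satellites (56 × 58.9% + 39 × 79.5% + 55 × 76.4% + 52 × 80.8%) / 202 = 73.3%. The assumed effect is the 0.2 reduction in the protocol's power statement.

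- PCAM: 81.4 − 20 × 0.370 = 74.0%
- Satellites: 73.3 − 20 × 0.161 = 70.1%
- Odds ratio: (0.740/0.260) / (0.701/0.299) = 1.22

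| True effect | Table 2 baselines | Both baselines 79.3% |
|---|---|---|
| 0 | 1.60 | 1.00 |
| −10 points | 1.38 | 0.89 |
| −20 points | 1.22 | 0.80 |

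Restricted to the first intervention period, the −20 point case gives 0.58 with Table 2 baselines (61.4% vs 73.3%) and 0.38 with equal baselines (59.3% vs 79.3%).

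**5. With the missing terms restored**

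A logistic fit to expected proportions with time-varying intervention, location and month gives an intervention odds ratio of 0.376 (Table 2 baselines) and 0.380 (equal baselines). The standardised differences are −20.1 and −20.0 points.

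**6. Calendar time alone**

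A linear-probability version with intervention and location but no month, under assumed downward trends of 0.5 and 1.0 points per month, returns −25.3 and −30.5 points for a true −20. With month included it returns −20.0 in both cases.

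**The case against.** The strongest reply is that Cohort was loose shorthand for exposure. Item 1 describes it as intervention versus control arms, and listing Location separately suggests that the authors meant two different things. A margin comment on the descriptive table also asks for cohort columns split into pre and post. On that reading, intervention is not missing and the duplication disappears. The possibility cannot be excluded, but section 2 and Unadjusted Analysis 2.a.i tie arm and cohort to site, and that same table heads its columns PCAM and Satellite. Calendar time would be missing on either reading.

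Other points on that side:

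- The Methods sentence names no intervention covariate either. This is correct. Exposure is implied there by model 3.a and by the stated comparison of intervention and non-intervention groups. The explicit conflict is over month, the repeated site term and the role of attending.
- Attending is probably meant as the clustering unit, as in 3.a and 3.b. This is fair, so the rank of 29 of 31 is conditional. The rank of 2 of 3 does not depend on it.
- The odds ratios come from a simplified model that the SAP does not propose, and the reversal of sign needs the Table 2 baseline gap. This stands, and the figures are illustrations only.
- Limiting 3.c to the first period would make arm equal exposure. No such limit is stated, and Cohort would still duplicate Location.
- The list is marked as open, and 3.b already gives a patient-adjusted intervention estimate. Both are true. They limit the consequence but do not reconcile the two definitions.

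**Conclusion.** The concern holds. Read with the SAP's own definitions, the 3.c and 4.b.ii list omits intervention received and calendar time, enters site twice, and cannot be followed together with the Methods text. The aliasing and the textual conflict need no assumed effect size.

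The numerical illustration shows that a working default could appear with an odds ratio on either side of 1 (1.22 or 0.80 for a true −20 points), depending on the baseline gap, and that the answer also changes with the window analysed. Steps 4 and 5 assume constant volume, no secular trend and no covariate imbalance. Table 2 includes SBRT courses and may include others that the protocol excludes, so the baseline gap is approximate. The slopes in step 6 are assumptions.

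The primary analysis is not at risk. What is at risk is the meaning of the sensitivity model and of the secondary result labelled as reduction. This should be corrected, but it does not undermine the trial's main conclusion.

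**What to change.** 1. Define 3.c as the primary model (time-varying intervention received, calendar month, location, clustering on attending) plus the listed patient and course covariates.
2. Delete Cohort, state that attending is the clustering unit, and make the list and the Methods text agree. Name the intervention term explicitly in Methods.
3. Build 4.b.ii on the same base model. Either report main effects as factors associated with the level of daily IGRT use or, if reduction is meant, add a small number of pre-named intervention-by-factor interactions labelled exploratory.

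The cost is SAP wording and a few model terms, with no new data. Any interaction estimates will be imprecise and should be presented as such.

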## 5. Study design

## 5.1 Design

In this study, we propose to leverage a pre-planned departmental initiative of default prescriptions to reduce unnecessary daily x-ray imaging in palliative radiation treatments.

This study follows a pragmatic stepped wedge design with two comparison groups: (1) a usual practice group (control group) and (2) a default radiation treatment prescription group (intervention group), in which the usual practice group will subsequently rollover from control to intervention. One group is comprised of physicians who practice at the Perelman Center for Advanced Medicine (PCAM). Another group is comprised of non-PCAM physicians at our network satellites (Pennsylvania Hospital, Chestnut Hill Hospital, Doylestown Hospital, and Valley Forge). As is standard practice for implementation of QI initiatives in our department, we will implement the intervention at one network site prior to implementing the intervention at all

[figure not shown]
sites. These groups will be assigned to the intervention or usual care at the start of the study by coin flip. Subsequently, the usual practice group will rollover into the default intervention.

Intervention. The default intervention will be started in February 2017. It will be comprised of default prescription order sets that do not include daily imaging for brain/ CNS, bone, and soft tissue metastases (See Figure 1). The defaults will be immediately preceded by a department wide session with intervention group physicians and therapy staff announcing the initiation of the intervention. Thus, as is usual practice in the department, physicians and department staff will be aware and educated on the QI initiative at the time of implementation. Default prescription order sets will be created in Aria (the radiation oncology electronic health record) for specific palliative treatment indications, namely brain/CNS, bone, soft tissue, and other palliative cases.

IGRT-LOCALIZATION INSTRUCTIONS:		
PRIMARY (Match for Treatment)	SECONDARY (EVAL)	
Modality: None	Modality: None	
Frequency: Other	Frequency: Other	
Match Instructions: Set up with attention to immobilization, tattoo markers, and weekly MV portal films	Additional / Special Instructions:	
Additional / Special Instructions: do not take KV-KV image		
Localization Instructions For CD Or Other If Different From Initial:		

Figure 1: Example of Default IGRT Prescription for Palliative Cases

Figure 2: Study Framework

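### The SAP's secondary multivariable list (4.b.ii) and sensitivity model (3.c) enter the PCAM-versus-satellite split twice and omit the intervention term, so neither can estimate the effect of the default

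*SAP*

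**What the plan says.** SAP 4.b.ii, the "Multivariate analysis for factors associated with reduction in daily IGRT", and SAP Adjusted Analysis 3.c, the sensitivity model, carry the same thirteen covariates. Item 1 is "Cohort (intervention vs. control arms", item 11 is Attending with no qualifier, and item 13 is "Location (PCAM vs. satellite". Neither list has an intervention-received term or calendar time.

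The SAP fixes the meaning of the arms in Study arms: "Intervention arm (Perelman Center for Advanced Medicine - PCAM" and "Usual practice / control group (Pennsylvania Hospital, Chestnut Hill", the latter continuing with the other satellites. Unadjusted Analysis 2.a uses cohort in the same sense: "Display graphically by month and cohort (PCAM vs. satellites".

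Models 3.a and 3.b are built differently. They use a separate Intervention term, Location and Time, and they qualify the physician term: "Attending (clustering at level of attending".

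The SAP Methods paragraph gives a third description. There the sensitivity analysis is the main model (GEE, attending as cluster, month and site as covariates) with patient characteristics added. A margin comment says that the sensitivity covariates may still change.

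**The concern.** A model cannot separate two names for the same column, so at least one of Cohort and Location is redundant in both lists. Attending as a set of fixed indicators would add a second redundancy, because the indicators within each group sum to that group's column. Software that zeroes redundant columns would still print a Cohort estimate, and its label invites reading it as the effect of the arm.

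The larger problem is what the lists leave out. Both groups have the default by the end of follow-up, so arm membership is not exposure. A sensitivity model without the exposure indicator and without time cannot confirm or challenge the primary estimate. The secondary analysis, for the same reason, cannot include the default among the factors associated with lower daily IGRT use.

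**Working it through.** No figure in the plan depends on these lists. The 89% power in Protocol section 9 belongs to the primary model, which has no Cohort term. The check is therefore on the structure of the design matrix.

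**Inputs.** About 29 physicians (Protocol 5.3); 623 PCAM courses and 56 + 39 + 55 + 52 = 202 satellite courses a year (Protocol Table 2); SAP calendar 2/10/16 to 10/10/17, which is 20 months; effect 0.2 (Protocol section 9). Assumed for illustration: an 18/11 split of physicians between PCAM and the satellites, which the documents do not give, and roll-out months excluded, as the SAP does in Unadjusted Analysis.

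**1. Cohort and Location.** Cohort = 1 for PCAM and 0 for satellites; Location is the same. Intercept + Cohort + Location has 3 columns and rank 2. This needs no assumption beyond the SAP's definitions.

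**2. Attending as fixed indicators, each attending in one group.** Intercept + Cohort + Location + 28 indicators has 31 columns and rank 29. Adding any constant c to the Cohort coefficient and subtracting c from every PCAM attending leaves all fitted values unchanged. With Location dropped and one reference attending per group, the printed Cohort coefficient is simply reference PCAM attending minus reference satellite attending.

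This was illustrated in one simulated dataset of 1,287 courses, with an assumed attending SD of 0.6 logits, default effect of -1.3 logits and site difference of 0.3. Four choices of reference pair gave Cohort coefficients of 0.59, -0.49, 2.62 and -0.84, all at log-likelihood -679.35. Over all 18 × 11 = 198 pairs the range was -2.29 to 2.89.

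If the between-attending SD is τ and the groups do not differ, the coefficient has SD √2·τ and the odds ratio has 95% range exp(±1.96·√2·τ):

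- τ = 0.7 (assumed): exp(±1.94), about 0.14 to 7.0
- τ = 1.5 (assumed): exp(±4.16), about 0.016 to 64

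The documents give no physician variance, so these ranges only show scale.

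**3. Attending as the GEE cluster only.** One of Cohort and Location survives, with a definite value. Its meaning follows from the calendar. PCAM has 12 unexposed and 7 exposed months (3/10/17 to 10/10/17), so 7/19 = 37% of its months are exposed. The satellites have 16 unexposed and 3 exposed months, so 3/19 = 16%. With constant monthly volume, no site difference and no time trend, a true reduction of 0.2 would appear as

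0.2 × (7/19 − 3/19) = 0.2 × 4/19 = 0.042,

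about one fifth of the effect. Any PCAM-satellite difference is added to that; in Protocol Table 2, PCAM stood at 81.4% and the satellites ranged from 58.9% to 80.8%. In the simulated data the Cohort log-odds with Location dropped was +0.171 (SE 0.145), although the default's effect had been set at -1.3.

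**4. With the terms of model 3.a.** Intercept + Intervention + Location + month (19 indicators) has 22 columns and rank 22, so Intervention is estimable. Adding 28 attending indicators gives 50 columns and rank 49. The lost dimension is Location within Attending; Intervention stays estimable.

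**The case against.** The strongest reply is that this is a duplicated line in a secondary list. If only Cohort and Location are aliased, software drops one and the other is a well-defined site contrast. The Methods paragraph has attending as the clustering unit and describes the sensitivity analysis as an extension of the main model, and a comment leaves the list open. Most of that stands, and it rules out two stronger readings.

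- A reader might infer that the arm coefficient is arbitrary under the plan as written. That also requires fixed attending indicators and no attending treating in both groups. Lists 3.c and 4.b.ii read the first way, but Methods does not. The second is implied by the Protocol 5.1 grouping ("Another group is comprised of non-PCAM physicians at our network satellites") but nowhere stated. With one cross-site attending, intercept + Location + Attending was full rank (30 of 30).
- A reader might infer that the primary result is compromised. Models 3.a and 3.b use Intervention, not Cohort, and the difference that Methods says will be reported compares intervention with non-intervention. Nor does any text say that the Cohort coefficient of 3.c will be reported as the effect of the default.

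A different defence is that Cohort was meant as exposure status, which is not aliased with Location (3 columns, rank 3). The SAP points the other way. It calls exposure Intervention in 3.a and 3.b, and the comment on the baseline table lays out cohort columns as PCAM and Satellite, each then split into pre and post.

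The Methods paragraph does not cure the lists either. It conflicts with 3.c and says nothing about 4.b.ii.

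**Conclusion.** The specification error is real and confined to a secondary and a sensitivity analysis. On the SAP's definitions Cohort and Location are the same variable in both lists, with certainty. What the remaining coefficient means depends on Attending. As fixed indicators with each attending in one group, neither Cohort nor Location is estimable. As the GEE cluster only, the survivor is a period-averaged site contrast that would carry about one fifth of the default's effect, under constant volume and no trend or site difference. In neither case is it the effect of the default, because the lists contain neither Intervention nor Time. The odds-ratio ranges hold only under the fixed-indicator reading, complete nesting and an assumed physician SD.

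**What to change.** In SAP 4.b.ii and 3.c:

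- Replace Cohort with the time-varying Intervention indicator of model 3.a.
- Add Time, defined as month as in the Methods paragraph. Model 3.b and its comment leave the definition open, so settle it there too.
- Keep Location once.
- State that Attending is the clustering unit only. If attending fixed effects are wanted instead, drop Location; Intervention remains estimable.
- Make 4.b.ii, 3.c and the Methods paragraph describe the same sensitivity model and the same patient covariates.

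Deleting Cohort alone is not enough: it removes the duplication but leaves a model with no intervention term.

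The cost is a few lines of SAP wording. No new data are needed, and the primary models do not change.
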